Given the nature of the HCP PLUS Peer Support group, it is not possible to guarantee full adherence from all of the patients. As a result, traditional ITT statistical methods might be biased due to the effects from non-adherent participants. To correct for this bias, we would implement an instrumental variable approach to estimate the effect of the intervention on the change in the HRQOL as measured by the SGRQ total score from baseline to 6-months post-enrollment.¹² One of the requirements for this analysis is to divide the group of patients assigned to the HCP PLUS Peer Support group into adherent and non-adherent participants. For our main analysis, we define as *adherent participants* all those patients who experienced at least 4 or more encounters with their peer mentor either by attending to a get-together, participated in a BREATHE call, or by having a phone conversation with their peer-pal. Phone conversations with peer-pals include both check-in conversations as well as conversations about the COPD related issues discussed at the get-togethers. For this analysis, we will instrument patient adherence with the patient's randomized assignment to either the control or the treatment group. Additionally, we will conduct sensitivity analyses by defining adherent participants to be (1) those participants with at least 2 encounters with their peers (get-togethers, BREATHE calls, or phone conversations) and (2) those participants who experienced at least 4 or more encounters with their peers either by attending to a get-together, participated in a BREATHE call, or by having a phone conversation with their BREATHE pal containing discussion of COPD-related issues (determination based on BREATHE pal notes.)

CACE: Secondary Outcomes

In order to analyze the effect of the Peer Support intervention on secondary outcomes such as the level of acute health care utilization (hospitalizations and ED visits), patient-reported outcomes (PROMIS scores), patient's activation measure, and HERTH hope index we will implement a CACE approach to control for the bias produced by not-fully adherent patients.

Just as with the case of our primary outcome, we will use a patient's randomization assignment as an instrument for HCP PLUS Peer Support group adherence. For this analysis we will define as

adherent participants all those patients who experienced at least four or more encounters with their peer mentor. We will also conduct sensitivity analyses in the same manner as for the primary outcome.

Intervention Implementation Analysis

In addition to assessing the primary and secondary outcomes for patients we intend to investigate which patient characteristics determine participation in the HCP PLUS Peer Support. That is, we will investigate which patient characteristics are related to attendance at BREATHE get togethers, participation in BREATHE calls, and phone interactions with BREATHE pals. As in the CACE analysis, we will define overall participation in the HCP PLUS Peer Support group as experiencing at least 4 or more encounters with a peer mentor either by attending a get-together, participating in a BREATHE call, or having a phone conversation. We will define participation in group support via attendance at 4 or more BREATHE get togethers or BREATHE calls. We will define participation in individualized 1:1 support by 4 or more encounters with a BREATHE pals over the phone. We will use multivariable logistic regression to predict overall participation, as well as participation in group or 1:1 support , from baseline characteristics such as age, gender, education level, distance from patient's home to meeting location, oxygen use, whether patient lives alone, whether patient reports they have a caregiver, self-reported health status, PAM level, and baseline assessments of hope, support, anxiety and depression from Herth Hope Index and PROMIS measures.

Heterogeneity of Treatment Effect (HTE) (PCORI Standard HT-1, HT-2, and HT-3)

HT-1, HT-3:

The goal of the HTE analyses in this study is to consider the difference in treatment effect between the two groups, taking into consideration differences in the groups that are not obviously accounted for in the balance created by the randomization scheme. Patient characteristics such as disease severity or caregivers' presence may show differences in the intervention's effect and thus are important avenues to explore for hypothesis generation. In these hypothesis generating HTE analyses, we will consider the following subgrouping variables for the primary outcome of change in SGRQ from baseline to 6 months: age (4 categories),

gender, disease severity (whether they are on continuous home oxygen), baseline PAM score (collapsed into low vs high levels), and caregiver presence (caregiver vs no caregiver). Within the HCP PLUS Peer Support group, we will also consider subgrouping by the propensity for adherence to treatment (collapsed into low vs high levels), with propensity for adherence to treatment as the estimated probability of adherence to treatment from our intervention implementation analysis described above.

HT-2, HT-3:

Subgroup treatment effects will be estimated by including a three-way interaction between the subgroup variable, the study assignment variable, and the 6-month time variable in a generalized linear mixed RE model. We will test for a difference in treatment effect between subgroups by a hypothesis test of the overall three-way interaction in this model. We will report estimates of subgroup treatment effects with corresponding 95% confidence intervals (CIs). For the comparison of propensity for adherence groups within the HCP PLUS Peer Support group, we will include an interaction between the subgroup variable and the 6-month time variable, test this interaction, and estimate subgroup effects with corresponding 95% CIs.

References

1. Jones PW. St George's Respiratory Questionnaire Manual. 2009;44(June):0-16.
3. PROMIS. Anxiety. A brief guide to the PROMIS Anxiety instruments. 2018:1-18.
4. PROMIS. Depression. A brief guide to the PROMIS Depression instruments. 2018:1-18.
5. PROMIS. Emotional Support. A brief guide to the PROMIS Emotional Support instruments. 2017:1-6.
6. PROMIS. Instrumental Support. A brief guide to the PROMIS Instrumental Support instruments. 2017:1-6.
7. PROMIS. Social Isolation. A brief guide to the PROMIS Social Isolation instruments.

2015:1-7.

8. PROMIS. Informational Support. A brief guide to the PROMIS Informational Support v2.0 instruments. 2015:1-7.

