healthcare professional (HCP) as the primary communicator about COPD self-management (Health Care Professional Arm), whereas the other uses a dual approach that involves both healthcare professionals and peer mentors delivering such communication (Health Care Professional PLUS Peer support Arm). Peer mentors are COPD patients and caregivers who have successfully managed COPD and have received foundational training on peer mentoring. Specifically we aim to: 1) Conduct a randomized controlled trial in which the 'HCP' and 'HCP PLUS Peer Support' strategies are tested in 'real-world' healthcare settings; 2) compare the impact of these strategies on patient satisfaction, experience, activation, self- efficacy, self-care behavior, health status, quality of life, use of Emergency Department (ED) and hospital services, and survival; and, 3) compare the impact of these strategies on caregiver satisfaction, experience, self-efficacy, stress, and coping skills. Study participants will be adult patients with moderate to severe COPD and their caregivers. Three hundred and twenty five patient participants will be recruited in 'real world' clinical settings from one urban and one suburban hospital and their specialty and primary care practices. Each patient will have the opportunity to include one family-caregiver with them in this study. The primary study outcome is the change in health-related quality of life at 6 months post-intervention compared to baseline. Secondary outcomes include: Combined number of COPD-related hospitalizations and ED visits, patient experience and satisfaction, patient-reported health status for physical, mental, and social well-being; symptom burden; patient activation and self- efficacy; medication adherence; smoking cessation rates; participation in pulmonary rehabilitation; physical activity levels; caregiver stress, coping skills, and self-efficacy. We hypothesize that the 'HCP PLUS Peer Support' strategy will achieve superior results compared to the HCP strategy.

2. Objectives (include all primary and secondary objectives)

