The overall goal of this proposal is to compare the effectiveness of two health communication and dissemination strategies that are designed to engage patients and family caregivers in successfully managing COPD in 'real-world' settings. Both strategies aim to advance patient understanding of COPD, its treatment options, and self-care tasks; support them in coping with the disease; and enable them to adopt a variety of positive behaviors, including adherence to treatment plans, smoking cessation, joining pulmonary rehabilitation programs, and assuming an active, healthy lifestyle. One strategy relies on the healthcare professional (HCP) as the primary communicator about COPD self-management (HCP Arm), whereas the other uses a dual approach that involves both healthcare professionals and peer mentors delivering such communication (HCP PLUS Peer Support Arm). Peer mentors are COPD patients and caregivers who have successfully managed COPD and have received foundational training on peer mentoring. Specifically we aim to: 1) Conduct a randomized controlled trial in which the 'HCP' and 'HCP PLUS Peer Support' strategies are tested in 'real-world' healthcare settings; 2) compare the impact of these strategies on patient satisfaction, experience, activation, self- efficacy, self-care behavior, health status, quality of life, use of Emergency Department (ED) and hospital services, and survival; and, 3) compare the impact of these strategies on caregiver satisfaction, experience, self-efficacy, stress, and coping skills.

The proposed study will answer the research question: Amongst COPD patients and their caregivers, would a dual strategy that combines healthcare professional and peer mentor delivery of COPD self-management education and support result in greater improvements in health status and quality of life, and reductions in acute healthcare services' utilization, compared to relying on healthcare professionals alone in these communications? Would such dual strategy result in reduced caregiver stress and improved coping and satisfaction?

3. Background (briefly describe pre-clinical and clinical data, current experience with procedures, drug or device, and any other relevant information to justify the research)

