We will follow the following procedures to ensure safety and track adverse events in this study: Adverse Events in this study will be identified and assessed for severity and tracked whether or not they are related to the study treatments. For the purposes of this study, serious adverse events include: death, hospitalization, or fall due to intervention related activities. These events will be assessed during routine data collection calls at 3, 6 and 9 months post enrollment. A log will be kept for unanticipated problems. Any participant deaths that occur within 30 days of receiving a study intervention, whether expected or unexpected, will be promptly reported in accordance with JHM policies. All pertinent adverse events will be included in the data reports to DSMB and to the IRB at continuing review time.

Study Measures and Outcomes

The primary outcome measure is change in health-related quality of life as measured by the Saint George's Respiratory Questionnaire (SGRQ) total score at 6 months post-intervention compared to baseline. Additional secondary patient outcomes that we will measure in this study include overall patient experience and satisfaction; patient activation; patient-reported health status; PROMIS informational support, emotional support, and social isolation domain measures; loneliness; anxiety and depression; and symptom burden. We will also measure the combined number of COPD-related and all cause hospitalizations and ED visits per patient at 6 months post-intervention start. Other

process/impact measures will include patient self- efficacy, and medication adherence; joining pulmonary rehabilitation; smoking cessation; caregiver stress, coping skills, and self-efficacy.

We will collect data on patient demographic characteristics, disease severity, co-morbidities, health literacy, history of healthcare utilization, anxiety and depression, mental health. Similarly, we will collect caregiver participants' age, gender, employment, relationship to patient, caregiving responsibilities, health status, and distance from patient home, and transportation means.

Below is a description of main patient study measures with comments on validity.

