Mortality		✓	✓	Mortality data collected from caregivers, hospital and ED records, and vital Statistics records
Caregiver Outcomes				
Family – caregiver preparedness for caregiving	✓	✓	✓	Preparedness for Caregiving Scale adapted from Understanding COPD questionnaire
Caregiver stress	✓	✓	✓	Zarit stress index, Ways of Coping Questionnaire
PROMIS measures	✓	✓	✓	PROMIS item bank- 2 domains will be used (each domain has 4 items): 1) Informational support; 2) Emotional support. There are 5 response options: Never, rarely, sometimes, usually, or always.
Patient and Caregiver Satisfaction and Experience			✓	Adapted from CAHPS plus additional intervention specific items

c. Statistical plan including sample size justification and interim data analysis.

We hypothesize that the dual strategy of using 'HCP PLUS Peer Support' to engage and support COPD patients and caregivers will have superior outcomes to the 'HCP only' strategy in the following areas: a) Improved health- related quality of life and survival, and reduced numbers of COPD-related hospital and ED visits; b) improved patient activation, self-efficacy, and self-care behaviors; c) improved self- efficacy and coping skills. These improvements will be noted at 3, 6, and 9 months compared to baseline.

The main analysis approach for assessing the change in the primary outcome measure from baseline, as well as changes in secondary outcome measures from baseline, will consist of performing analyses of the treatment effect between the two study groups under intention to treat, adjusted for baseline measure, site, and recruitment setting. The health- related quality of life in hypothesis (a) will be measured using the SGRQ. For Hypothesis (b) patient activation will be measured using PAM, self- efficacy and self- care behaviors will be measured using the 'Understanding COPD questionnaire', Morisky scale, and additional items on physical activity, smoking cessation, and participation in pulmonary rehabilitation. For hypothesis (c), caregiver self- efficacy will be measured using 'Preparedness for caregiving' scale and an adapted 'Understanding COPD questionnaire' items for caregivers; and, coping skills will be measured using the 'Ways of Coping Questionnaire'.

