The study will compare the impact of these strategies on the outcomes of health-related quality of life, mortality, and use of Emergency Department (ED) and other hospital services, as well as intermediate measures such as patient activation, self- efficacy, and self-care behavior, as described in the BREATHE2 Study Conceptual Model shown in Figure 1 below. At the same time, the study will compare the impact of these strategies on caregiver self-efficacy, stress, and coping skills. We will also assess both patient and caregiver experience and satisfaction within the HCP PLUS Peer Support Group.

[figure not shown]

Figure 1. BREATHE2 Study Conceptual Model

Study Design (PCORI Standard IR-1)

Phase 1 of this study involved intervention development followed by peer mentor recruitment and training. Phase 2 of this study, which is addressed by this SAP, involves rigorous testing of the study intervention in a randomized controlled trial (RCT) at two study sites: (1) Johns Hopkins Bayview Medical Center (JHBMC) and affiliated pulmonary and primary care clinics and (2) Howard County General Hospital (HCGH) and affiliated pulmonary and primary care clinics. (some of these clinics are part of Johns Hopkins Community Physicians). Thus within each study site, patients were recruited from two clinical settings: (1) inpatient recruitment within the hospital and (2) outpatient recruitment from the affiliated clinics.

We consented and enrolled 290 persons who met the initial eligibility criteria of receiving a physician diagnosis of COPD and treatment for it. Patient participants were randomized to one of the two study groups in this trial (HCP or HCP PLUS Peer Support) and their respective Caregiver Participant, if they have one enrolled, participated with them in that study group. Then patients were randomized 1:1 to the HCP or the HCP PLUS Peer Support.

Our primary study outcome is the change in quality of life (QOL) over the 6 months post discharge. Other patient measures include patient activation self-efficacy, self-care behavior,

health status, used of Emergency Department (ED) and other hospital services, and survival. Caregiver measures include caregiver self-efficacy, stress, and coping skills.

Intervention Description

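### The SAP assesses satisfaction and experience within the HCP PLUS Peer Support arm and plans no between-arm analysis, although Aims 2 and 3 promise one

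*Combined protocol and SAP*

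**What the plan says.** **Protocol.** Section 2 (Objectives) gives Aim 2 as to "compare the impact of these strategies on patient satisfaction, experience, activation, self- efficacy, self-care behavior, health status, quality of life", continuing to acute care use and survival. Aim 3 is to "compare the impact of these strategies on caregiver satisfaction, experience, self-efficacy, stress, and coping skills". The research question in the same section asks: "Would such dual strategy result in reduced caregiver stress and improved coping and satisfaction". Section 4, under Study Measures and Outcomes, states: "Additional secondary patient outcomes that we will measure in this study include overall patient experience and satisfaction; patient activation; patient-reported health status". The outcomes table in section 7b has one row for patient and caregiver satisfaction and experience, ticked at one time point. Its instrument is described as "Adapted from CAHPS plus additional intervention specific items". None of these places limits the measure to one arm.

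**SAP.** The Study Description first commits to a caregiver comparison: "At the same time, the study will compare the impact of these strategies on caregiver self-efficacy, stress, and coping skills". The next sentence changes the verb and the population: "We will also assess both patient and caregiver experience and satisfaction within the HCP PLUS Peer Support Group". The Study Objectives, the list under Study Outcomes and Hypotheses, and the Statistical Analysis section do not mention satisfaction or experience again.

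**The concern.** The aims ask whether adding peer support changes how satisfied patients and caregivers are. That needs both arms. Everyone in the trial receives the one-hour session with the respiratory care practitioner and the educational materials, and the peer arm receives the peer programme on top. A satisfaction score from the peer arm alone mixes the two components and has nothing to be set against.

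If the SAP is followed as written, the report will contain a one-arm satisfaction figure where the aims led readers to expect a comparison. If a comparison is added later, it will have no pre-specified model, items or visit.

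**Working it through.** The check is a comparison of texts, followed by a short calculation of what a two-arm comparison could detect.

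**1. What the aims promise and what the SAP specifies**

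| Measure | Aim | Between-arm plan in the SAP |
|---|---|---|
| Quality of life, acute care use, survival, activation, self-efficacy, self-care behaviour (patients) | 2 | Yes, as hypotheses under Study Outcomes and Hypotheses |
| Health status (patients) | 2 | Named under Study Design, not itemised |
| Satisfaction, experience (patients) | 2 | None; assessed within HCP PLUS |
| Self-efficacy, stress, coping (caregivers) | 3 | Announced in Study Description, not itemised |
| Satisfaction, experience (caregivers) | 3 | None; assessed within HCP PLUS |

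Aim 2 names 6 + 1 + 2 = 9 measures and Aim 3 names 3 + 2 = 5. Satisfaction and experience are therefore 2 of 9 and 2 of 5.

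**2. Whether the general rule for secondary outcomes fills the gap**

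Protocol section 7c and the SAP's Statistical Analysis section both give secondary outcomes a mixed model. It is adjusted for the baseline value, and the treatment effect is read from group-by-time interactions. The section 7b table ticks satisfaction at one time point and shows no baseline. With no baseline value there is nothing to adjust for, and with one visit there is no time interaction to test. The rule cannot be applied to this measure as it stands, so a between-arm comparison needs its own specification. Neither document gives one.

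**3. Whether the within-arm wording is just loose**

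In one paragraph the SAP speaks of comparing the strategies on patient outcomes, then on caregiver outcomes, and then of assessing satisfaction within one group. The change of wording is specific, and nothing later in the SAP reverses it.

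**4. What a two-arm comparison could detect**

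Inputs from protocol section 7c: 145 patients per arm, 15% attrition, alpha 0.05 and power 0.80. I assume a two-sided test, because the sides are not stated, and that the attrition figure applies to the satisfaction visit.

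- Patients: n per arm = 145 × 0.85 = 123.25. The detectable standardised difference is (1.960 + 0.842) × √(2/123.25) = 0.36.
- Caregivers: the documents do not say how many patients enrol one. With an assumed share f, n per arm = 145 × f × 0.85:

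| Assumed share with a caregiver | n per arm | Detectable standardised difference |
|---|---|---|
| 20% | 24.6 | 0.80 |
| 30% | 37.0 | 0.65 |
| 50% | 61.6 | 0.50 |
| 70% | 86.3 | 0.43 |

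The patient comparison would be informative. The caregiver comparison would be less precise and is best reported as an estimate with its interval.

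**The case against.** The strongest reply is that the SAP sentence does not exclude the HCP arm. It does not contain the word only. The protocol makes patient experience and satisfaction a secondary outcome, and section 7c promises a between-group analysis of secondary outcomes. Experience within the peer arm is also a legitimate descriptive measure: the instrument includes intervention-specific items that only peer-arm participants could answer, and the SAP attaches no efficacy claim to it.

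Much of this stands. The documents do not show that HCP participants were not asked the general items, so a comparison may well be feasible. Within-arm reporting suits the peer-programme items. It does not remove the conflict: the aims promise a comparison, the SAP describes something else, and the general model does not fit the measure.

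A reader might go further and infer that the SAP has no caregiver comparison at all and that Aim 3 is wholly untested. The text does not support that. The SAP commits to comparing caregiver self-efficacy, stress and coping. Caregivers are surveyed at enrolment and at 3, 6 and 9 months without arm restriction, and the protocol supplies instruments and a general between-arm model. A reader might also think that the caregiver hypothesis was exchanged for patient activation. In fact the SAP splits protocol hypothesis (a) into two, so that protocol (b) becomes SAP (c), and the caregiver item drops off the list.

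**Conclusion.** The conflict is real and limited. Satisfaction and experience, for patients and for caregivers, have no between-arm analysis in the SAP although Aims 2 and 3 promise one. That is four entries of the 14 across the two aims (2 + 2 of 9 + 5). It would be wrong to conclude that Aims 2 and 3 cannot be answered. Six of the nine Aim 2 measures have between-arm hypotheses in the SAP, and three of the five Aim 3 measures have a stated between-arm intent. The primary outcome is untouched.

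The secondary point is one of completeness. The caregiver comparison announced in the Study Description appears in neither the Study Objectives nor the outcome list, and both should carry it.

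The conclusion assumes that the SAP sentence means what it says. Whether the comparison can be rescued depends on whether the HCP arm was asked the general items, which the documents do not settle.

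**What to change.** 1. Replace the within-arm sentence in the SAP's Study Description with a between-arm comparison of the general CAHPS-based items, run separately for patients and for caregivers. Use a regression on study group, adjusted for site and recruitment setting, at the single follow-up visit, with no baseline term and no time interaction. Name the visit and list the items. If it is the 9-month visit, say how late enrollees are handled, since the SAP expects no 9-month data from them.
2. Report only the peer-programme-specific items within the HCP PLUS arm, labelled descriptive.
3. If the HCP arm was not asked the general items, state that satisfaction and experience are single-arm and descriptive, and remove the comparison from Aims 2 and 3 and from the research question.
4. Add the caregiver outcomes to the SAP's objectives and outcome list, each with its instrument and time points. For protocol hypothesis (c) these are Preparedness for Caregiving, the adapted Understanding COPD items and Ways of Coping. From the outcomes table, add the Zarit index and the two caregiver PROMIS domains. These have a baseline and repeated visits, so the existing mixed model suits them.

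The cost is SAP text and a few more tables. No new data are needed if both arms were asked the general items.
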